### **Visit 2**

The following will happen at this visit:

Potential subjects will be instructed to refrain from regular oral hygiene regimen for 24 hours and eating for 4 hours before the appointment in the study. The study staff will

Version 061020

update of Inclusion/Exclusion Criteria, medical history, and concurrent medications.

Whole-mouth Plaque Index (Navy PI) and Gingival Abrasion Score will be evaluated by a qualified examiner following visualize dental plaque with a disclosing agent (Mira-2-Ton, Miradent) and record the scores on the Case Report Form for the baseline information. Successively, standardized dental digital photographs of three close-up views of the retracted views for plaque area measurement: front, left and right lateral sides.

Assigned toothbrush and a fluoride toothpaste will be given to each subject. the study staff will instruct Bass method to each subject (without using a toothbrush) and provide the assigned toothbrush with a half inch length of the toothpaste. Subjects will brush their teeth for 2 minutes with Bass method under a supervision of the study staff. Whole-mouth Navy PI and Gingival Abrasion Score will be recorded, and standardized dental digital photographs will be taken again for immediate post-brushing evaluation.

Subjects will then be instructed to use assigned product to use 2 times daily, after breakfast and before bedtime, for one week for 2 minutes with instructed brushing method. They will maintain a daily diary of their product usage. Compliance will be assessed by subject diary.

Next appointment will be scheduled within 7 days  $\pm$  one day. Subjects will be instructed to refrain from regular oral hygiene regimen for 24 hours and eating for 4 hours before the appointment in the study. They will be advised to follow the instructions carefully and return to the study center with their assigned toothbrush and diary for their next examination.

### **Visit 3**

After one week, subjects will return to the office to return the used toothbrush and their dairy. The following will happen at this visit:

The study staff will update of inclusion/exclusion criteria, medical history and concurrent medications. Adverse experiences will be noted and recorded during the study.

Whole-mouth Navy Plaque Index and Gingival Abrasion Score will be evaluated by a qualified examiner following visualize dental plaque and record. Then, standardized dental digital photographs of three close-up views of the retracted views: front, left and right lateral sides.

Subjects will follow their normal oral hygiene using a toothbrush and a toothpaste for "wash-out" period given at Visit 1.

Next appointment will be scheduled to return within 7 days  $\pm$  one day, and subjects will be instructed to refrain from regular oral hygiene regimen for 24 hours and eating for 4 hours before the appointment in the study.

### **Visit4**

After a 1-week washout, subjects will return to the office to begin the second period of the

[figure not shown]
Version 061020

study, using the same study procedures and be assigned the alternate toothbrush as in Visit 2.

At the end of Visit 5 (examination for the second product) they will go through a 1 week wash out period and then return for Visit 6 (baseline for the third product).

Rustogi Modified Navy Plaque Index (Rustogi et al. J Clin Dent. 1992)

After disclosing dental plaque on teeth, the Rustogi Modified Navy Plaque Index (Navy PI) is evaluated as either present or absent (1 or 0) on each of the nine areas of the buccal and lingual tooth surfaces except for third molars. Whole tooth, marginal, and approximal areas are defined as shown below. Score of each area (from A to I) will be recorded for further assessments. In this study, the PI should be evaluated by only trained and calibrated examiners.

[figure not shown]

Gingival Abrasion Score (Van der Weijden et al. J Clin Periodontol. 2004)

After the gums were dried with compressed air, Mira-2-Ton® disclosing solution was applied for better visualization of areas where the surface of the oral epithelium had been abraded. The gingival tissues were divided into three areas: marginal (cervical free gingiva), interdental (papillary free gingiva) and mid-gingival (attached gingiva).

The lesions were assessed as small (<5 mm), medium (3-5 mm) and large (>5 mm) using a periodontal probe. Those lesions measuring between 2 and 3 mm were assigned a score of small or medium according to nearest mm mark on the probe.

Version 061020

#### Standardized Digital Dental Photographs A4J

[figure not shown]
Dental photographs will be taken by a digital SLR camera (model, maker) with a ring flash to distribute the light evenly with intraoral exposure. A macro lens (85 mm or more) will be used to take a close-up photo.

To standardize the exposing views, the same magnification (1:1 or 1:2 views) and same views at the same distance from the subject shall be used for all subjects and all visits.

Study staffs will expose the cheek retracted views. Retracted views from front, left and right lateral will be taken at the same setting. When an image of the front of the mouth is taken, the subject's bicuspids may be focused on to obtain the overall sharpness. Images from left and right lateral may be centered between the cuspid and the first premolar.

A length of tooth height (mm) of one of maxillary central incisors will be recorded using a periodontal probe for future analyses.

After image acquisition with same spatial resolution and contrast resolution for an existing image analysis software, the image of each non-molar tooth will be assessed. The entire visible tooth area and the area of plaque of each tooth will be calculated into either  $\text{mm}^2$  or number of pixels.

Version 061020

### **XIII. ADVERSE EXPERIENCES**

#### **Adverse Event Definition and Handling**

An adverse event is any unexpected or serious medical occurrence in a clinical investigation subject during the study, whether or not related to the study product. All adverse events observed by the investigator and/or reported by the subject will be recorded throughout the entire study and documented. The Investigator will be asked to make a judgement on all adverse events as to their severity and possible relation to the study treatments.

More specifically, adverse events would include:

- Any unexpected event not seen before study initiation.
- Any pre-existing event that recurs with increased intensity or increased frequency subsequent to initial product treatment.

Adverse events will be reported to the investigator and the sponsor will be notified within 24 hours of any serious adverse events. All adverse events should be recorded on the appropriate case report form, including date of onset, severity, duration, treatment and follow-up observation.

The following definitions will be used for grading severity of adverse events:

- Mild - Either asymptomatic, or subject is aware of the sign, symptom or event, but it is easily tolerated.
- Moderate - Discomfort enough to cause interference with usual activity and may warrant intervention.
- Severe - Incapacitating with inability to do usual activities.

The investigator will make an assessment of the likelihood that there is a reasonable possibility of a causal relationship between a study product and the adverse event. This will be captured using the following criteria: product related, non-product related, non- product related but protocol related. The causal relationship to the product will be assessed as: definitely related, probably related, possibly related, probably not related or definitely not related.

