## XVI. STATISTICAL ANALYSIS AND DATA MANAGEMENT

Since this study is a Proof of Concept study, the sample size calculation was not performed.

Descriptive statistics for all subjects will be performed for background and demographic variables. Continuous variables are expressed as frequencies (n), mean +/- SD and categorical variables are expressed as frequencies (n) and percentages (%).

Student *t* test or Wilcoxon *rank sum* test where appropriate, will be used to compare among different bristles. For intragroup changes of endpoints before/after one-time brushing or use for one-week, paired *t* test or Wilcoxon signed rank test will be used where appropriate. Spearman Rank Order Correlation was used to analyze correlations between the variables.

Safety parameters will include oral soft and hard tissues and subjective reports as well as any AEs. The analysis will include all observed effects which initially occurred or worsened following treatment. Any adverse effects will be summarized classified according to their intensity (mild, moderate, or severe) and relationship (definitely related, probably related, possibly related, probably not related or definitely not related) to study product.

All statistical tests will be conducted using Minitab 18.

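### The adverse event definition is narrower than the safety analysis it feeds, events are not tabulated by brush, and the tissue safety item has no scheduled examination beyond the abrasion score

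*Combined protocol and SAP*

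**What the plan says.** Section XIII (Adverse Event Definition and Handling) opens with the definition: "An adverse event is any unexpected or serious medical occurrence in a clinical investigation subject during the study". Two bullets then spell out what is meant: "Any unexpected event not seen before study initiation" and "Any pre-existing event that recurs with increased intensity or increased frequency subsequent to initial product treatment". The duty to record is tied to that definition: "All adverse events observed by the investigator and/or reported by the subject will be recorded throughout the entire study and documented". The lowest severity grade is described as "Either asymptomatic, or subject is aware of the sign, symptom or event, but it is easily tolerated". The items to be entered on the case report form include onset date, severity and duration; the brush in use is not among them.

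Section XVI describes the safety analysis in three sentences. The parameters are: "Safety parameters will include oral soft and hard tissues and subjective reports as well as any AEs". The scope is: "The analysis will include all observed effects which initially occurred or worsened following treatment". The tabulation is: "Any adverse effects will be summarized classified according to their intensity (mild, moderate, or severe) and relationship" to study product. No breakdown by brush, period or sequence is mentioned.

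Table 2 schedules the gingival abrasion score at Visits 2 to 7 and again immediately after brushing at Visits 2, 4 and 6, and adverse event recording at Visits 2 to 7. Section XV makes the one-week change in abrasion score the fourth secondary outcome.

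**The concern.** Every subject is to use all three brushes, and the purpose of the study is to compare bristle types. If the brushes differ in tolerability over one week, the difference is plausibly in mild, local and foreseeable effects. A definition that turns on an event being unexpected or serious leaves out that kind of effect when it is new.

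Three things follow. The analysis calls for data that the recording rule does not require. The events that are recorded have no planned table showing which brush was in use. And one of the named safety parameters has no dedicated examination behind it. What is at stake is the completeness and usefulness of the safety report, not the efficacy result.

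**Working it through.** The documents state no safety figure to reproduce and no event rate to calculate from. The check sets the sections side by side.

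1. **Definition against analysis.** Consider an effect that is new, foreseeable and not serious.
   - Opening definition (Section XIII): it is neither unexpected nor serious, so it is not covered.
   - First bullet: limited to unexpected new events, so it is not covered.
   - Second bullet: has no expectedness limit, but applies only to pre-existing events, so it is not covered.
   - Recording duty: applies to adverse events as defined, so it does not reach this effect.
   - Section XVI scope: has no expectedness limit, so the effect belongs in the analysis.

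   The recording rule is therefore narrower than the analysis. The mild grade does not close the gap, because an event is graded only once it has met the definition. The references to adverse experiences in Section VII and under Visit 3 carry no wider definition; Section XIII, which bears that title, supplies the only one.

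2. **Summary by brush.** Section XVI classifies by intensity and by relationship to study product. In Section VII the three sequences are A-B-C, B-C-A and C-A-B, so a table that does not name the brush pools three products. The information can be recovered: onset date, visit dates and the assigned sequence place each event in a test period or a wash-out. No such table is planned, and there is no rule for events that start in a wash-out.

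3. **Tissue and subjective parameters.**
   - Table 2 and the visit procedures in Section XII contain no examination of soft and hard oral tissues as such.
   - The soft-tissue lesion item in the exclusion criteria is an eligibility judgement at baseline. The update of eligibility criteria at later visits is also a screening check, not a recorded safety assessment.
   - The diary in Section X is described as a record of brushing times, and no scheduled symptom question appears. Subjective reports can therefore enter only through adverse event recording, which returns to step 1.

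4. **What the abrasion score already covers.** Scores per subject: 6 (Visits 2 to 7) + 3 (after brushing at Visits 2, 4 and 6) = 9, or 9 / 3 = 3 per brush. The one-week change is a listed outcome, and Section XVI plans tests between bristles. Visible abrasion is thus measured whatever the adverse event definition says. Two limits remain: the score does not capture soreness or sensitivity, and the immediate post-brushing abrasion scores are collected but are not among the outcomes listed in Section XV.

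**The case against.** The strongest reply is that the protocol already measures the most obvious local harm of a toothbrush. That stands. A reader might infer from the definition that foreseeable gum effects in general will go unreported; the documents do not support this, because abrasion is scored systematically and its one-week change is an outcome. A reader might also infer that adverse events cannot be compared between brushes. That goes too far as well: the brush can be worked out from onset date and sequence, and only the planned table is missing. Nor can it be said that no visit looks at soft tissue, since the abrasion score is a soft-tissue measure. What is missing is any wider soft-tissue examination and any hard-tissue one.

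It can further be argued that the definition is merely loose: there is no list of expected effects, the bullets may be read as illustrations, and Section XVI shows a broad intention. It is true that treating soreness or sensitivity as expected is an assumption of this review, and that a careful investigator might record such events anyway. But the expectedness limit is stated twice, in the definition and in the first bullet, and a statement of analysis scope does not oblige anyone to record an event. The conflict is between two stated rules.

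Finally, this is a proof-of-concept study in 10 subjects with one week of use per brush, so any table by brush would be descriptive. That limits what the change can deliver, but the change is also very cheap.

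**Conclusion.** The concern holds in a limited form. New, foreseeable, non-serious effects other than scored abrasion fall outside the adverse event definition although the planned analysis includes them. No summary by brush is planned, although one can be derived. The soft and hard tissue parameter has no scheduled examination beyond the abrasion score.

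This is a safety-reporting gap. The primary plaque outcomes are unaffected. Its size in events cannot be stated, because the documents give no rate for mild gum effects and do not say which effects count as expected. The conclusion assumes that site staff apply the definition as written and regard effects such as soreness or sensitivity as foreseeable with a new brush. If staff record everything in practice, the loss shrinks to the missing table and the unmatched tissue parameter.

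**What to change.** - **Section XIII:** remove the expectedness limit from the definition and from the first bullet. Define an adverse event as any untoward medical occurrence, expected or not and related or not, so that recording matches the scope in Section XVI.
- **Section XVI, tabulation:** add that events are tabulated descriptively by the brush in use at onset. Show wash-out events separately, labelled with the last test brush used; they should not simply be counted against that brush, because subjects use a different supplied toothbrush in the wash-out. Show events before the first test brush, including those in the wash-out after Visit 1, as pre-treatment.
- **Section XVI, parameters:** replace the soft and hard tissue item with the gingival abrasion score already collected, including the immediate post-brushing scores, as the soft-tissue safety measure. Hard-tissue findings would then be reported as adverse events if they arise.

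These are wording changes in two sections, with no new visit or procedure. The cost is a few more mild events to record. With 10 subjects the table by brush supports description only and should carry no formal test.

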#### **Serious Adverse Event**

A serious *adverse event* is *any adverse event that:*

- Results in death
- Is life threatening (i.e., immediate risk of death as the event occurred). A life-threatening event does not include an event that, had it occurred in a more severe form, might have caused death, but as it occurred did not create an immediate risk

Version 061020

of death. For example, hepatitis that resolved without evidence of hepatic failure would not be considered life threatening even though hepatitis of a more severe nature can be fatal. Similarly, an allergic reaction resulting in angioedema of the face would not be life threatening, even though angioedema of the larynx, allergic bronchospasm or anaphylaxis can be fatal.

- Results in persistent or significant disability or incapacity (i.e., a substantial, persistent disruption in a subject's ability to conduct normal life functions).
- Requires inpatient hospitalization or prolongation of an existing hospitalization. Hospitalization or prolongation of a hospitalization constitutes criteria for an adverse event to be serious; however, it is not in itself considered a serious adverse event. In the absence of an adverse event, a hospitalization or prolongation of a hospitalization should not be reported as a serious adverse event by the participating Investigator. This is the case in the following situations:
  - The hospitalization or prolongation of hospitalization is needed for a procedure required by the protocol.
  - The hospitalization or prolongation of hospitalization is part of a routine procedure followed by the center. This should be recorded in the study file.

In addition, a hospitalization for a pre-existing condition that has not worsened does not constitute a serious adverse event.

- Results in cancer
- Results in a congenital anomaly or birth defect.

Additionally, important medical events that may not result in death, be life-threatening, or require hospitalization may be considered a serious adverse event when, based upon appropriate medical judgment, the event(s) may jeopardize the subject and may require medical or surgical intervention to prevent one of the outcomes listed in this definition. Examples of such medical events include allergic bronchospasm requiring intensive treatment in an emergency room or at home, blood dyscrasias or convulsions that do not result in hospitalization, or the development of drug dependency or drug abuse. If there is any doubt whether the adverse event constitutes a serious adverse event, the information will be treated as a serious adverse event.

#### **XIV. SUBJECT COMPLETION AND WITHDRAWAL**

##### **Subject Completion**

Only subjects who complete all procedures and comply with all areas of the protocol will be deemed to have completed the study. Subjects will be compensated for their time and travel and for successfully completing all provisions and procedures of the study. If a subject voluntarily withdraws from the study, or if withdrawn by the Investigator for any reason, he/she will be compensated on a pro rata basis. Subject compensation will be

Version 061020

documented in the Informed Consent and will be approved by the IRB.

### **Subject Withdrawal**

Subjects are free to withdraw at any time during the clinical trial. Subjects may also be withdrawn from the study at any time at the discretion of the Investigator. All subject withdrawals will be documented in the study file. Where possible, the reason for the withdrawal will be documented. Any withdrawals as the result of an adverse event will be followed-up at the discretion of the Study Investigator. Withdrawn subjects will not be replaced.

### **Subject Discontinuation**

A subject will be considered discontinued from the study at any time under the following circumstances:

- Any subject who violates any condition of the entrance criteria after having been entered into the study
- Any subject who develops a confounding concomitant illness (as determined by the subject, Research Coordinator, or Investigator) or a serious adverse event
- Any subject who becomes uncooperative, does not adhere to the requirements of the study protocol, or refuses to complete the study

## **XV. EFFICACY**

### **Primary Outcome Variables**

The primary outcome variables to be assessed are:

- 1) the reduction of plaque index (Navy PI) for interdental area after one-time brushing in a whole mouth.
- 2) the reduction of digitally measured interdental plaque area on non-molar teeth, facial/buccal aspect after one-time brushing by image analysis.

### **Secondary Outcome Variables**

- 1) the change of plaque index for interdental area in a whole mouth one week after using the toothbrushes.
- 2) the change of digitally measured interdental plaque area on non-molar teeth one week after using the toothbrushes.
- 3) correlation between plaque index and plaque area by image analysis in non-molar teeth, facial/buccal aspect.
- 4) The change of gingival abrasion score in whole mouth at one week after using the toothbrushes.

Version 061020

As necessary, additional exploratory statistical data analysis may be performed to further advance evaluation of the results.

## XVI. STATISTICAL ANALYSIS AND DATA MANAGEMENT

Since this study is a Proof of Concept study, the sample size calculation was not performed.

Descriptive statistics for all subjects will be performed for background and demographic variables. Continuous variables are expressed as frequencies (n), mean +/- SD and categorical variables are expressed as frequencies (n) and percentages (%).

Student *t* test or Wilcoxon *rank sum* test where appropriate, will be used to compare among different bristles. For intragroup changes of endpoints before/after one-time brushing or use for one-week, paired *t* test or Wilcoxon signed rank test will be used where appropriate. Spearman Rank Order Correlation was used to analyze correlations between the variables.

Safety parameters will include oral soft and hard tissues and subjective reports as well as any AEs. The analysis will include all observed effects which initially occurred or worsened following treatment. Any adverse effects will be summarized classified according to their intensity (mild, moderate, or severe) and relationship (definitely related, probably related, possibly related, probably not related or definitely not related) to study product.

All statistical tests will be conducted using Minitab 18.

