## III. STUDY OBJECTIVES

The primary objective of this study is to evaluate and compare toothbrushes with three different bristle types in the reduction of plaque index (**PI**) for interdental area and digitally measured interdental plaque area after one-time brushing.

Secondary objectives are to evaluate toothbrushes with three different bristle types in the changes of PI, digitally measured interdental plaque area and gingival abrasion one week after using the toothbrushes, and to assess an agreement between the different evaluation methods (**PI** and a plaque area by image analysis)

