## VI. SUBJECT POPULATION

### **Number of Subjects**

A total number of 10 subjects will be enrolled. Volunteers must read and sign the Informed Consent Form after the nature of the study has been fully explained.

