## **VII. STUDY DESIGN OVERVIEW**

This cross-over group, examiner blinded, randomized, single center study will enroll subjects to target 10 subjects completing the study. Subjects will visit the clinical site 7 times including screening/enrollment visit. Subjects will be instructed to refrain from regular oral hygiene regimen for 24 hours and from eating for four hours before each appointment. The study examiner and staff will screen for subjects that meet the enrollment criteria. Subjects will be randomly assigned to one of three treatment groups. The study staff responsible for random assignments will be blinded to the product treatments.

- Group 1: A -> B -> C
- Group 2: B -> C ->A
- Group 3: C ->A-> B

After distribution of an assigned test toothbrush, subjects will receive a basic brushing instruction for Bass method by a study staff but without actual brushing. Subjects will perform toothbrushing using the assigned product for 2 minutes under supervision. Plaque Index (Navy PI), Gingival Abrasion Score and standardized digital dental photos will be taken before/after the one-time brushing.

Subjects will use the assigned toothbrush for a week until the next visit for evaluation. At the visit, the used toothbrush shall be returned to the study staff to avoid mixing up with next test product. PI and Gingival Abrasion Score will be recorded, and the standardized digital dental photos will be taken. After one week of wash-out period, subjects will return to the clinical site to start the next test product. The study schedule is showed in Table 2. Subjects will be instructed to keep a diary given by the study staff at Visit 1 throughout the study. Adverse experiences will be noted and recorded during the study.

Version 061020

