## **IX. TREATMENT REGIMEN**

Qualified subjects meeting all inclusion and exclusion criteria will be provided their assigned toothbrush (A, **B** or C) at Visit 2, 4 and 6 for use for immediate post-brushing evaluation and during the one-week treatment phase of the study. Subjects will be instructed to brush their teeth as instructed with their assigned toothbrush 2 times daily (after breakfast, before going to bed) for 2 minutes, using only the provided toothpaste for one-week study period.

Following their one week of use, they will then go through a one-week "washout" period and will follow their normal oral hygiene using study provided toothbrush and fluoride toothpaste. The same fluoride toothpaste will be used throughout the whole study period. Subjects will refrain from using other oral hygiene products throughout the study period.

Version 061020

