## **XII. STUDY PROCEDURE**

### **Screening and Enrollment Visit (Visit 1)**

Potential subjects will be instructed to refrain from regular oral hygiene regimen for 24 hours and eating for 4 hours before the appointment in the study.

Male and female subjects will read and sign the informed consent prior to enrollment. Subjects will be asked about demographics, medical history, general health status and current medication usage, and the information will be recorded.

Plaque Index (Quigley and Hein) of a whole mouth will be evaluated to verify that the subjects meet the inclusion and exclusion criteria (average PI>2).

If the participants meet the study criteria, they will be assigned to one of three treatment groups randomly based on computer generated randomized numbers.

Subjects will be instructed to use a toothpaste and a toothbrush (for wash-out period) provided by the study staff until the next visit. The appointment of next visit will be scheduled within 7 days ± one day.

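### The primary between-brush comparison is assigned to independent-group tests, although every subject uses all three brushes

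*Combined protocol and SAP*

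**What the plan says.** Section VII describes the design: "This cross-over group, examiner blinded, randomized, single center study will enroll subjects to target 10 subjects completing the study". Its three sequences (ABC, BCA, CAB) each contain all three brushes. Section IX has qualified subjects receive a brush "at Visit 2, 4 and 6 for use for immediate post-brushing evaluation and during the one-week treatment phase of the study". Every completer therefore contributes one reduction per brush. The subject number in Section VI is fixed: "A total number of 10 subjects will be enrolled".

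Section III sets the question: "The primary objective of this study is to evaluate and compare toothbrushes with three different bristle types in the reduction of plaque index", together with the digitally measured interdental plaque area, after a single brushing. Section XV lists the same two reductions as primary outcomes.

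The only statement of how brushes are compared is in Section XVI: "Student *t* test or Wilcoxon *rank sum* test where appropriate, will be used to compare among different bristles". The next sentence begins "For intragroup changes of endpoints before/after one-time brushing or use for one-week, paired" and goes on to name the t test in its paired form and the signed rank test. Section XVI gives no alpha, power or effect size and no within-subject correlation. It has no subject or period term.

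**The concern.** Student's t test in its usual form and the rank sum test both assume that the two samples come from different people. Here any two brushes are compared on the same 10 people, so each pairwise test would treat 10 subjects as 20 independent ones. The two consecutive sentences in Section XVI show that the authors distinguish paired from unpaired tests and place the primary comparison in the unpaired family.

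A cross-over is chosen so that differences between people drop out of the treatment comparison. The planned tests leave that variation in the error term. In a study this small the likely result is that a real difference between bristle types is missed. Changing to a paired test once the data are seen would be a post hoc change to the primary analysis.

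**Working it through.** **Inputs from the documents.** 10 subjects (Sections VI and VII); three brushes per subject (Sections VII and IX); unpaired t or rank sum between brushes (Section XVI). The plan has no power or sample-size figure to reproduce.

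**Assumptions, not in the documents.** Two-sided 5%; 10 complete pairs; normal reductions with equal SD (σ); no period effect; within-subject correlation of the reductions (ρ) from −0.2 to 0.7; true differences of 0.5, 0.8 and 1.0 SD.

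**Standard error of the difference between two brush means.**

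- Planned formula: √(2σ²/n) = √(2/10) = 0.447σ.
- Correct formula: √(2σ²(1−ρ)/n). At ρ = 0.5 this is √(0.1) = 0.316σ.
- Ratio of planned to correct: 1/√(1−ρ). At ρ = 0.5 this is 1.41.

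**Error rate and power.** The planned test is the pooled t with 18 df (critical value 2.101), evaluated by simulation. The paired test has 9 df (critical value 2.262). Its power comes from the noncentral t with noncentrality δ√n/√(2(1−ρ)), where δ is the true difference in SD units. For δ = 0.8 and ρ = 0.5 that is 0.8 × 3.162/1 = 2.53, giving 61.6%.

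| ρ | SE planned/correct | Type I error, planned | Power at 0.8 SD, planned | Power at 0.8 SD, paired |
|---|---|---|---|---|
| 0 | 1.00 | 5.0% | 40% | 36% |
| 0.1 | 1.05 | 4.0% | 39% | 39% |
| 0.3 | 1.20 | 2.3% | 38% | 48% |
| 0.5 | 1.41 | about 1% | 37% | 62% |
| 0.7 | 1.83 | 0.2% | 35% | 83% |

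At ρ = −0.2 the ratio is 0.91 and the type I error of the planned test is 7.1%.

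**Other effect sizes, planned vs paired.**

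- 0.5 SD: 18.5% vs 17.1% (ρ = 0), 15% vs 22% (0.3), 12% vs 29% (0.5), 8% vs 45% (0.7).
- 1.0 SD: 56% vs 51% (ρ = 0), 57% vs 66% (0.3), 59% vs 80% (0.5), 61% vs 95% (0.7).

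**Rank tests.** The standard-error ratio applies to the t test only, but the rank sum reference distribution also rests on independence. Its type I error is 4.3%, 1.9%, 0.9% and 0.2% at ρ = 0, 0.3, 0.5 and 0.7. Power at 0.8 SD, rank sum vs signed rank, is 35% vs 35%, 33% vs 46%, 32% vs 60% and 31% vs 81%.

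**The case against.** Student's t might loosely include the paired form, and the plan says to choose where appropriate. This reading fails. The next sentence names the paired t separately for another purpose, the rank sum test has no paired reading, and the choice offered is only between t and rank sum. The general allowance in Section XV for exploratory analyses does not repair a primary test.

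The stronger objections concern size:

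- **Direction.** With positive ρ the error is conservative, so a significant result would not be undermined. This stands. The anti-conservative case needs negative ρ, for which the documents give no support.
- **Unknown ρ.** The loss is nil at about 0.1 and large only from about 0.5. Since the outcomes are reductions, ρ may be lower than for raw plaque scores. This also stands.
- **Proof of concept.** The study makes no power claim, so the harm could be called lost efficiency. That status explains why there is no sample-size calculation. It does not justify a test that contradicts the design.
- **Period effects.** A plain paired test is not fully protected. Take a 4/3/3 split with four subjects on ABC, ρ = 0.5 and an assumed linear drift of 1 SD from period 1 to period 3. The paired t test of B against A then has type I error of about 2% and power at 0.8 SD of 49%, not 62%. The paired figures above therefore hold only without period effects, which favours the model offered in the fix.
- **Incomplete pairs.** Section XIV does not replace withdrawals, and a paired test drops anyone missing either brush. With 8 pairs, paired power at 0.8 SD is 38% (ρ = 0.3) or 50% (0.5).

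These points limit the size of the gain. None of them makes the independent-group test match the design.

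**Conclusion.** The concern holds. The primary between-brush test does not fit the cross-over, and its p value is right only if ρ is zero, an assumption that the choice of design rejects. With positive ρ the consequence is lost power rather than false positives: at 0.8 SD, about 10 percentage points at ρ = 0.3 (48 − 38) and 25 at ρ = 0.5 (62 − 37). These figures rest on the assumptions listed in the working, chiefly an unknown ρ, 10 complete pairs and no period effect.

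The correction does not make the study large. Paired power for a 0.5 SD difference is still only 22% at ρ = 0.3 and 45% at ρ = 0.7. It should still be made before the data are analysed, because it concerns the primary comparison and needs only a change of wording.

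**What to change.** **Required.** In Section XVI, replace the sentence on comparing bristles with wording such as: *Reductions after one brushing, and one-week changes, will be compared between brushes with the paired t test, or the Wilcoxon signed rank test where appropriate, on within-subject differences between brushes.*

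**Preferable.** Fit one linear model per outcome with brush and period as fixed effects and subject as a blocking effect. Ten subjects cannot be split equally over three sequences, so period effects do not cancel exactly. With a 4/3/3 split (four on ABC) the simple B − A mean carries [4(P2−P1) + 3(P1−P3) + 3(P3−P2)]/10 = 0.1 × (P2−P1), where P1 to P3 are the period effects. Section XII says that "they will be assigned to one of three treatment groups randomly based on computer generated randomized numbers" and mentions no blocking. A 6/2/2 split would carry 0.4 × (P2−P1).

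**Optional.** Add the pre-brushing score of the same period as a covariate.

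**Cost.** Wording only, with no extra subjects, visits or data. Section XVI already plans paired t and signed rank tests for another purpose. Each paired test has 9 df instead of 18, which costs about 4 points of power at 0.8 SD if ρ is 0. With 30 complete observations the model leaves 29 − 9 − 2 − 2 = 16 residual df, of which the period term takes 2.
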